3.2 Exclusion Criteria

1. Patient must not have past history of radiotherapy within the projected treatment field.
2. Advanced symptomatic heart failure as defined as NYHA Class IV heart failure (inotrope dependent and/or current left-ventricular assist device (LVAD))
3. Polymorphic VT or ventricular fibrillation (VF) as a clinical heart rhythm (as determined by 12-lead ECG and/or ICD interrogation).

4. More than 3 distinct clinical VT morphologies observed (ECG or ICD interrogation or invasive EP study) OR more than 5 distinct induced VT morphologies during ECGI testing.
5. Advanced myocardial scar substrate that would require stereotactic delivery to a target volume deemed unsafe by the treating physician.
6. Unlikely to live 12 months, in the absence of VT, as best based on clinical judgment by the treating and enrolling physicians.
7. Patient must not be pregnant and/or breastfeeding and must have a negative pregnancy test within 14 days of study entry.

4.0 TREATMENT PLAN

4.1 Noninvasive Imaging for Scar/Fibrosis, Edema, Inflammation

To maximize the potential benefit and minimize the risks of noninvasive radioablation, we will perform extensive imaging of cardiac ventricular scar or inflammation harboring the VT circuit using clinically available imaging tests, including magnetic resonance imaging (MRI), positron emission testing (PET), and myocardial perfusion imaging (MPI/SPECT) when available. If these studies have been performed previously within one year, additional testing is not needed. Refer to Section 7.0 Study Calendar for anticipated timing of clinical cardiac imaging modalities. The role of each test and potential risk to each is described briefly below.

4.1.1 Magnetic Resonance Imaging (MRI)

When coupled with administration of IV contrast agent (gadolinium), cardiac MRI is the gold-standard imaging study for detailed evaluation of the distribution of fibrosis and scar. In this study, MRI will be performed prior to the procedure (baseline study) to help determine the target volume for radioablation using the best-practices to safely acquire the data and the latest sequences for artifact-reduction, called Wideband sequences (55, 56).

Immediately after treatment (day 3), MRI will be used to evaluate for the presence of local edema at the treated site (T2-weighted imaging) and to screen for acute injury, such as pericardial effusion.

MRI will be performed again 3 months after the treatment to evaluate for any changes in cardiac fibrosis and scar from the baseline study. It will also screen for

potential toxicities, including changes in myocardial function, valvular performance or pericardial effusion.

This type of serial MRI has never been performed after administration of cardiac radiotherapy, and the results are expected to provide important insight into the mechanisms and timing of the radiobiological effect of this treatment. We perceive this knowledge to be of utmost importance in determining the projected time course of the safety and clinical effect for future patients receiving this type of therapy.

We anticipate that most or all of the patients who are enrolled into this study will have cardiac defibrillators (ICDs) to treat ventricular arrhythmias. Historically, the presence of an ICD has been a contraindication to performing MRI for various theoretical and observed concerns. Over the course of the past decade, great strides have been made to safely allow patients with ICDs to undergo MRI scans. These are reviewed in several recent publications (42-53). The most prominent of these is the completion of a large registry to characterize the risks of undergoing MRI with a cardiac device (MAGNASAFE.org). This registry and other publications (50) have defined the substantial safety margin of MRI use in patients with cardiac devices, and these studies form the basis for an upcoming professional guideline statement regarding the expanded and safe use of MRI in patients with cardiac devices (anticipated 2016 release). In short, the MAGNASAFE registry was a multicenter trial of 1,500 patients with cardiac devices who underwent MRI scanning on a 1.5 T scanner. Of the 1500 MRI scans, only 1 patient developed a clinical event (generator failure due to inappropriate sensing) which was deemed to be caused by inappropriate ICD programming. The overall positive results of the MAGNASAFE study have resulted in the national CMS National Coverage Determination (NCD) allowing for coverage of MRIs in patients with cardiac devices if they are performed in a research study that meets CED (coverage with evidence development) criteria.” (Medicare website: CAG-00399R2). Since the release of MAGNASAFE, a number of trials including patients who are specific to our population (patients with VT, with implanted ICD, undergoing cardiac MRI) have been published (42-53). In these studies, there were no adverse effects of cardiac MRI with appropriate pre-scan ICD programming, further supporting the overall safety of this scan in the appropriately selected patients.

A second major advance is the development of MRI-conditional cardiac devices, which are now commercially available from several manufacturers (Medtronic, Biotronik). Whenever possible, we plan to use these devices for new implants at our hospital. However, we expect most patients who enroll into this study will have older legacy devices, which do not have specific MRI-conditional labeling.

In this study, we recognize the potential risks involved with MRI in patients with ICDs, and these risks will be shared with patients in full disclosure, using language

and images from a recently published “Cardiology Patient Page” article (54). MRI remains the gold standard for assessment of fibrosis and edema, and we believe the large benefits of precision guidance of radiotherapy outweigh the small potential risks of ICD system changes. Patients who are unwilling to accept these risks, or patients in whom we believe the risks to be excessive will not undergo MRI. We will then use clinically available imaging, such as nuclear MPI/SPECT, which is less specific and sensitive than MRI.

Patients in whom we will NOT offer an MRI include:

- a) Newly implanted ICD system (any component added < 6 weeks)
- b) Dependence on ICD system for pacing (complete heart block or severe sinus node dysfunction without ventricular escape)
- c) Presence of abandoned, fractured or epicardial cardiac leads
- d) Active noncardiac implanted device (other than cardiac device)
- e) Abdominal position of cardiac device
- f) Battery voltage of ICD at elective replacement interval
- g) Increased risk to administration of IV gadolinium such as renal impairment (estimated glomerular filtration rate (eGFR) < 40) or previous adverse reaction to IV gadolinium.
- h) Patient preference

For patients who undergo MRI, several safeguards have been developed as “best practices” and will be used for this study. These include:

- a) Supervision of appropriately trained personnel for the duration of the MRI scan
- b) Pre-treatment and post-treatment ICD device checks
- c) Pre-treatment ICD programming per standardized protocol (MAGNASAFE registry) to minimize chances of untoward ICD effects, including asynchronous or inhibited pacing mode (VOO/DOO or VVI/DDI setting), disabling magnet response, disabling episode memory, and disabling therapies for tachyarrhythmia. A full risk-mitigation protocol has been developed and is available as a supplement to this protocol.

[figure not shown]
4.1.2 Positron Emissions Testing (PET)

PET uses a special camera to measure specific signal in heart cells emitted from injected radioisotopes (called tracers). The amount of radiation received from PET is small, and the risk of procedural complication is exceedingly low. In this study, the radioisotope will be Fludeoxyglucose (FDG). This isotope tests for areas of inflammation and ischemia, which may be particularly important in patients with nonischemic reasons for cardiomyopathy. The FDG-PET imaging will be done in all patients, unless contraindicated due to previous adverse reaction. The

information gained from FDG-PET cardiac metabolism will be combined with the scar imaging from MRI to help guide radioablation.

4.2 Noninvasive Electrical Imaging

The method of electrocardiographic imaging (ECGI) is described in Section 1.5 above. Graphically, it is illustrated below:

In brief, the patient undergoes a CT scan while wearing a “vest” of electrodes that record heart beats. The electrical information from the surface of the body can then be computed onto the patient-specific heart model to noninvasively display the characteristics of the imaged heartbeat. Useful information includes: where the beat begins, how it depolarizes the heart, which parts of the heart have abnormal signals from previous heart attacks or scar. Fitting the vest of electrodes on the patient, obtaining electrical signals, and performing the CT scan is generally completed in under 30 minutes.

In this study, prior to treatment, patients will undergo ECGI during a noninvasive-programmed stimulation (called NIPS) procedure. A NIPS procedure is a commonly performed procedure in the cardiac electrophysiology lab. The patient receives light IV sedation for the procedure, and vital signs are monitored closely. Communication with the patient’s ICD is established, and the ICD is used to intentionally induce ventricular tachycardia through basic pacing maneuvers. Once the VT is induced, a 12-lead ECG and 256-lead ECGI are obtained (less than 10 seconds). The ICD is then again used to pace-terminate the VT (less than 10 seconds).

In this study, the NIPS will be performed in a standardized fashion. In the fasting state, single, double, and then triple extrastimuli will be delivered to refractoriness at drive trains of 600 and 400 ms, via the right ventricular ICD lead. Results from

the NIPS will yield electrical information (ECG and ECGI) that guides targeting of the noninvasive ablation to the areas of origin of the ventricular arrhythmias.

Despite the perceived risk of intentionally inducing a potentially life-threatening arrhythmia, NIPS is considered a rather low-risk procedure in the EP lab. Common risks include:

- Hypotension or adverse reaction to IV sedation (usually propofol);
- Induction of an arrhythmia that cannot be terminated by pacing, requiring external cardioversion/defibrillation or use of the ICD is necessary to restore regular rhythm

Contraindications for NIPS include:

- Because of the possibility for cardioversion/defibrillation, the most common contraindication for NIPS is the presence of atrial fibrillation in a patient that cannot receive anticoagulation
- Hemodynamic or medical instability prior to procedure
- ICD at elective replacement interval (ERI) or end of service (EOS)

During follow-up after treatment, ECGI will be performed as a standalone procedure, without the need to perform NIPS.

4.3 Targeting the Area for Noninvasive Ablation

The clinical cardiac electrophysiologist will determine the region of the heart to be targeted for noninvasive ablation on an individual patient basis. The decision combines: A) scar architecture from cardiac MRI; B) inflammation location from PET; C) 12-lead ECG interpretation; D) 3-dimensional ECGI interpretation, using previously published criteria for origin of VT; E) anatomic considerations from CT scan; F) reduced cardiac motion or myocardial thinning, suggestive of previous cardiac injury or scar. As a general rule, efforts will be made to target all areas of VT origin and adjacent scar or inflammatory regions that harbor related circuits. In almost all cases, the targeted area will avoid areas of healthy tissue and focus on areas that demonstrate severely reduced cardiac motion.

4.4 Radiation Therapy Guidelines

4.4.1 Dose, Fractionation

Radiotherapy will consist of stereotactic body therapy to be given over one fraction. Patients will be planned for a dose of 25 Gy in a single fraction to the PTV.

4.4.2 Simulation Procedures/Patient Positioning

Patients will be immobilized using a system (such as BodyFIX) that is known to keep immobilization setup uncertainty to ≤ 3 mm. All patients will undergo free breathing CT simulation using thin (≤ 3 mm) slice thickness CT. An additional respiratory correlated 4D-CT will be acquired and co-registered to the planning CT for purposes of assessing respiratory motion. IV contrast will be used to facilitate definition of cardiac structures when not otherwise contraindicated. Esophageal contrast will be used to facilitate definition of the esophagus and upper stomach when not otherwise contraindicated. Additional clinical images may be co-registered to the planning CT based on availability and at the discretion of the clinician.

4.4.3 Target Volumes

The treatment target will be defined using radiation oncology principles of target definition. The gross target volume (GTV) will be segmented through corroboration of all previously acquired imaging (MRI, CT, SPECT, etc.) and EP data (12-lead EKG, prior catheter mapping, ECGI, etc.). An internal target volume (ITV) will be created based on the 4D-CT to account for any impact on the summative effect of respiratory and averaged-out cardiac motion. No clinical target volume (CTV) expansions will be utilized. The PTV will be generated at the discretion of the treating physician based on immobilization, machine uncertainties, and setup uncertainty, but should generally range between 0.3 cm and 0.7 cm.

4.4.4 Treatment Planning

All patients will be planned to a target dose of 25 Gy in a single fraction to the PTV, subject to organ at risk (OAR) dose constraints. Coverage goal of the PTV will be for $\geq 95\%$ of the PTV to be covered by $\geq 95\%$ of the prescription dose, although in situations where a critical OAR structure is violated, coverage of PTV will be compromised in order to meet dose constraints.

Dose limits are being employed as means to minimize the likelihood of toxicity, but true tolerance to OARs are not well described for single fraction schemes to the central thorax, and therefore prioritization will be employed for planning purposes taking into account the balance between PTV coverage and relative consequences of toxicity to specific OARs.

Priority	Definition
1	Obey spinal cord constraints. No deviations allowed.
2	Respect PTV coverage requirements.
3	Respect OAR constraints. If the PTV is next to or involving an OAR (not the spinal cord), then likely the guideline constraints cannot be met. In such cases, dose to OAR should not exceed 105% of

	prescription dose and effort should be made to avoid treating the entire circumference of the structure (particularly trachea, bronchus, esophagus).
--	------------------------------------------------------------------------------------------------------------------------------------------------------

4.4.5 OAR Contouring

In order to verify dose limits to OARs, OARs must be contoured such that appropriate volume histograms can be generated. Instructions for the contouring of these organs are as listed in the table below. An OAR may be omitted from contouring and subsequent evaluation in the DVH if it is > 10 cm from the PTV, or at the discretion of the treating radiation oncologist if it is determined that no clinically meaningful dose will be received by the OAR.

Serial Tissue	Contouring	Volume	Volume Max (Gy)	Max Point Dose (Gy)**
Spinal Cord and medulla	Entire bony canal	<0.35 cc <1.2 cc	10 Gy 8 Gy	14 Gy
Spinal Cord Subvolume (5-6 mm above and below level treated per Ryu)		<10% of subvolume	10 Gy	14 Gy
Esophagus*	Include the mucosal, submucosa, and all muscular layers out to the fatty adventitia	<5 cc	11.9 Gy	15.4 Gy
Heart/Pericardium	Contoured along with the pericardial sac. The superior aspect (or base) for purposes of contouring will begin at the level of the inferior aspect of the aortic arch (aorto-pulmonary window) and extend inferiorly to the apex of the heart.	<15 cc	16 Gy	22 Gy
Great vessels	The wall and lumen of the named vessel	<10 cc	31 Gy	37 Gy
Trachea and Large Bronchus*	Contour the trachea and cartilage rings starting 10 cm superior to the PTV extending inferiorly to the bronchi ending at the first bifurcation of the named lobar bronchus.	<4 cc	17.4 Gy	20.2 Gy
Rib		<5 cc	28 Gy	33 Gy
Skin	The outer 0.5 cm of the body surface anywhere within the whole body contour.	<10 cc	25.5 Gy	27.5 Gy

Stomach	The entire stomach wall and the gastric contents included from the GE junction to the proximal duodenum at the pylorus.	<5 cc	17.4 Gy	22 Gy
Parallel Tissue		Critical Volume (cc)	Critical Volume Dose Max (Gy)	
Lung (Right & Left)	Contour right and left lung as one structure including all parenchymal lung tissue but excluding the GTV and major airways (trachea and main/lobar bronchi)	1500 cc	7 Gy	
Lung (Right & Left)		1000 cc	7.6 Gy	V-8Gy <37%
Liver	Contour right and left lobes as one structure including all parenchymal liver tissue but excluding the GTV and major draining ducts, extrahepatic portal vein, and gall bladder.	700 cc	11 Gy	

4.5 Evaluability Guidelines

Patients who complete the full intended dose of single fraction SBRT are evaluable for both the primary and secondary objectives.

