4.8 Duration of Therapy

Because this study involves administration of a single fraction of SBRT over the course of approximately 10 minutes, there is no option for discontinuation of treatment once initiated.

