9.0 MEASUREMENT OF EFFECT

1. Acute (≤ 90 days) safety of ENCORE will be defined as a $\leq 20\%$ rate of protocol-specific serious or serious adverse events (SAEs) using CTCAE v4.0 criteria that are possibly/probably/definitely related to study treatment, based on previously published data for expected invasive catheter-based VT-ablation procedures. Early stopping rules have been created such that if 5 or more patients develop ENCORE related SAEs out of the first 10 patients, this would be deemed significantly greater than 20% ($\alpha < 0.05$), and the trial will be halted.
2. Preliminary efficacy of ENCORE will be defined by the number of subjects with a reduction in ICD therapies (six month period before ENCORE treatment compared to six month period after ENCORE treatment) as adjudicated by continuous ICD monitoring.

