11.0 STATISTICAL CONSIDERATIONS

11.1 Early Stopping Criteria

Through a one sample test for proportions, assuming a maximal clinically acceptable SAE rate of 20%, 5 or more SAEs out of the first 10 patients would be significantly greater than 20% ($\alpha < 0.05$). As such, the protocol will be halted if 5 or more of the first 10 patients develop a SAE.

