11.3 Analytic Plan for Primary Objectives

SAEs defined by CTCAE v4.0 criteria within 90 days of ENCORE that are possibly/probably/definitely related to study treatment will be recorded. ENCORE therapy will be deemed safe if the rate of SAEs is $\leq 20\%$. An additional early stopping rule dictates that if 5 or more out of the first 10 patients develop ENCORE related SAEs, the trial will be halted.

The number of ICD therapies delivered in the 6 month periods preceding and following ENCORE therapy will be recorded for each patient by interrogation of the ICD. ENCORE therapy will be deemed efficacious if there is a reduction in ICD therapies before and after treatment. The proportion of patients with efficacious ENCORE therapy will be calculated, with the intent of demonstrating at least 40% efficacy.

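### Section 4.5 makes full-dose completion the evaluability condition for safety as well as efficacy, so a patient whose SBRT is interrupted could be left out of the 90-day SAE rate

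*Combined protocol and SAP*

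**What the plan says.** Section 4.5 is the only evaluability statement in the text available: "Patients who complete the full intended dose of single fraction SBRT are evaluable for both the primary and secondary objectives". Under section 2.1 the first primary objective is acute safety up to 90 days. Under section 2.2 the secondary objectives include late toxicity. One completion-based sentence therefore covers safety and efficacy alike.

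Section 11.3 says that "SAEs defined by CTCAE v4.0 criteria within 90 days of ENCORE" with at least a possible relation to treatment will be recorded, and that the therapy is deemed safe if their rate is at most 20%. It does not say which patients form the denominator, and no separate safety population is defined.

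Section 4.8 describes a single fraction of about 10 minutes and says "there is no option for discontinuation of treatment once initiated".

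The early stopping rule appears three times. Section 9.0 has "if 5 or more patients develop ENCORE related SAEs out of the first 10 patients", section 11.3 has "if 5 or more out of the first 10 patients develop ENCORE related SAEs, the trial will be halted", and section 11.1 has "the protocol will be halted if 5 or more of the first 10 patients develop a SAE". None of the three mentions evaluability.

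**The concern.** Whether a patient completes the dose is known only after exposure has begun, and an acute event can prevent it. A safety rate restricted to completers can therefore lose a patient because of the event that the rate is meant to count. If the interruption is caused by a treatment-related SAE, the loss lowers the observed rate.

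The patients enter with refractory VT or a heavy PVC burden with cardiomyopathy (section 3.1), so an emergency during delivery is conceivable. With 19 patients and a fixed 20% cut-off, a single patient's status can decide the primary safety verdict. If the plan is silent, that status would be settled after the outcome is known.

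**Working it through.** **Inputs.** 19 patients; SAE rates of 5% and 20%; stated power 75.4% and alpha 0.0829 (section 11.2). Safety criterion of at most 20% (section 11.3). Stopping at 5 or more of the first 10, with alpha below 0.05 (section 11.1).

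**Step 1: reproduce the plan's figures.** The section 11.2 safety figures correspond to a rule of at most 1 SAE in 19.
- Alpha: P(X ≤ 1 | 19, 0.20) = 0.8^19 + 19 × 0.2 × 0.8^18 = 0.0144 + 0.0685 = 0.0829, as stated.
- Power: P(X ≤ 1 | 19, 0.05) = 0.95^19 + 19 × 0.05 × 0.95^18 = 0.7547. The plan prints 75.4%, which agrees up to truncation.
- Stopping rule: P(X ≥ 5 | 10, 0.20) = 0.0328, below 0.05 as stated.

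These figures use all 19 patients, and all of the first 10 for the stopping rule. Section 11.2 makes no allowance for non-evaluable patients.

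**Step 2: exclude one affected patient under the 20% criterion.** The comparison is k/19 against (k − 1)/18.

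| Affected, k | All treated | One affected patient excluded | Verdict |
|---|---|---|---|
| 3 | 3/19 = 15.8%, safe | 2/18 = 11.1%, safe | unchanged |
| 4 | 4/19 = 21.1%, not safe | 3/18 = 16.7%, safe | reversed |
| 5 | 5/19 = 26.3%, not safe | 4/18 = 22.2%, not safe | unchanged |

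For one excluded affected patient, only k = 4 reverses the verdict. Excluding a patient without an SAE (after a machine fault, say) moves the rate slightly the other way: 3/19 = 15.8% becomes 3/18 = 16.7%, still safe.

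**Step 3: sensitivity, on an assumption.** Suppose a share q of patients with a related SAE is removed because delivery was interrupted. The documents give no q, and section 4.8 implies that it is near 0. With true SAE rate p, safe meaning at most 3 of 19, and the stopping rule ignored, P(declared safe) = P(X ≤ 3 | 19, p(1 − q)). The denominator is kept at 19. The limit stays at 3 for any denominator from 15 (3/15 = 20%) to 19 (3/19 = 15.8%), so this simplification matters little.

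| p | q = 0 | q = 5% | q = 10% | q = 20% |
|---|---|---|---|---|
| 20% | 0.4551 | 0.4995 | 0.5451 | 0.6380 |
| 30% | 0.1332 | 0.1656 | 0.2035 | 0.2968 |

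The direction is always toward safe. The size is negligible if q is near 0.

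**Step 4: effect on the design.** If every patient who receives any SBRT is counted, n = 19, alpha = 0.0829, power = 0.7547 and the stopping-rule alpha of 0.0328 all stand. If one patient were dropped and the limit of 1 SAE kept, n = 18 would give alpha 0.0991 and power 0.7735.

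**The case against.** **The sentence in 4.5 does not exclude anyone in so many words.** A reader might infer that only full-dose patients are evaluable. Literally, the sentence gives a sufficient condition and does not say how a partly treated patient is handled. This stands as a point of wording. But it is the sole rule in a section on evaluability, so the ordinary reading is that other patients are not evaluable. On the literal reading their status is undefined. Either way the same clarification is needed.

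**Partial delivery is not foreseen.** Section 4.8 makes the case an edge case, and this largely stands. It does not say how an emergency or a machine interruption would be counted. A completion condition in 4.5 has work to do only if non-completion can occur.

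**The event would be captured anyway.** Section 7.0 schedules adverse-event assessment at the treatment visit and on day 3, section 5.8 covers attributable grade 3 to 5 toxicities, and section 10.0 provides for ongoing monitoring and a toxicity summary. An event on the table would be recorded and seen. That answers any worry about concealment, but recording an SAE does not place the patient in the rate.

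**The stopping rule.** A reader might also infer that such a patient drops out of the 5-in-10 count. The documents do not support this: all three statements of the rule count the first 10 patients with no evaluability condition. They do not say whether those 10 are enrolled or treated patients, which is a reason to confirm the set but does not show a fault.

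**Conclusion.** The point holds as an ill-chosen safety denominator for an uncommon event. The only evaluability rule conditions the primary safety objective on completing the dose, and nothing in 11.3 overrides it. If an affected patient were left out, the error would favour a conclusion of safety. The illustrated reversal, from 21.1% to 16.7%, requires exactly four affected patients among 19, one of them excluded for incomplete delivery.

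The conclusion rests on the ordinary reading of 4.5 and on an interruption being possible despite 4.8. It would be tempting to say that the trial's SAE rate is biased downward. The documents do not support that, because they give no frequency of partial delivery and no link between interruption and related SAEs. The plan permits such a bias but does not establish that one occurs. Early stopping is not shown to be affected.

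**What to change.** In sections 4.5 and 11.3, state that all patients who receive any SBRT are included in the 90-day related-SAE rate and in late toxicity. Confirm in 9.0, 11.1 and 11.3 that the first 10 patients for the stopping count are drawn from the same set. Keep the full-dose rule for the efficacy set only, and list any patients excluded from it with the reason.

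The cost is about one sentence in each section. No extra data are needed, and the planned sample size, alpha and power are unchanged.
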